
2) Protocol Title

Partnering with WIC to prevent excessive weight gain in pregnancy

3) Investigator

[name], MPH

4) Objectives

a. Primary specific aim: To determine whether the healthy lifestyle program lowers the prevalence of excessive gestational weight gain, compared to usual WIC care. Primary hypothesis: Participants randomized to the healthy lifestyle intervention arm will demonstrate significantly lower prevalence of excessive gestational weight gain, compared to those randomized to usual WIC care.

b. Additional aims:

- i. To compare trial arms with respect to changes in diet and physical activity, and rates of adverse pregnancy outcomes (including glucose intolerance, hypertension, and infant macrosomia).
- ii. To utilize the RE-AIM framework to evaluate the intervention's dissemination potential in WIC. We will assess: reach into the patient population; effectiveness on outcomes; organizational adoption; consistency of implementation; and maintenance of effects on 6- and 12-month maternal/child postpartum weights.
- iii. To quantify the intervention's cost-effectiveness.

5) Rationale and Significance

Nearly two-thirds of pregnant women exceed Institute of Medicine (IOM) weight gain guidelines.¹ Excessive gestational weight gain not only adversely affects the current pregnancy – by increasing risk of diabetes and hypertension, cesarean delivery, and infant macrosomia – but it also promotes new or persistent obesity in women and their children.^{2,3} Ethnic minority women are at particular risk of greater gains because they are more likely to enter pregnancy obese,⁴ reside in obesogenic environments,⁵ and adopt obesity promoting behaviors (e.g., high caloric intake, physical inactivity).⁶⁻⁸ However, these high risk women also suffer from a paucity of treatments. Without intervention, the implications are clear: most will exceed recommended gains in pregnancy and incur significant morbidity for themselves and their children.^{9,10}

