- i. **Primary outcome.** *The primary outcome is the proportion of women with excessive gestational weight gain*, defined as the proportion of mothers exceeding weekly Institute of Medicine (IOM) weight gain targets (>0.32 kg/week for BMI 25-29.9 kg/m²; >0.27 kg/week for BMI ≥ 30 kg/m²) over the study period (from enrollment to end of pregnancy).⁵⁷ Total gestational weight gain will be calculated as the difference between weight in kilograms measured at 36-38 weeks' gestation (end of pregnancy) and weight at the baseline visit (in the first trimester or early second trimester of pregnancy). Weight in clinical gowns, without shoes, will be recorded in duplicate by trained staff using high-quality, calibrated SECA digital scales. We will also use BodyTrace scales for patients seeking a remote option (and/or during restrictions to in-person visits during the Covid-19 pandemic) that will be sent to the participant after completion of the combined CS/EN call. In the rare case that a mother delivers her infant before 36-38 weeks' gestation, we will abstract her last prenatal weight from her obstetric chart and call her within 2 weeks of delivery to administer our follow-up

survey. We expect to abstract weights in <10% of mothers based on previous experiences with the target population. Height will be measured to the nearest 0.1 cm using a calibrated stadiometer at participants' in-person baseline assessments or via self-report via phone.

ii. **Secondary and patient-centered outcomes.**

1. ***Dietary intake*** will be measured using the Automated Self-Administered 24-hour (ASA24) dietary assessment tool, a web application developed by NCI.⁶⁹ We will collect one 24-hour dietary recall during combined CS/EN visit or call and during the end of pregnancy visit. Data are summarized as intake of micro- and macronutrients, food groups, and dietary patterns. ASA24 has been validated against more expensive, time-consuming tools.⁷¹ We have experience using this measure in diverse groups.^{48,49}

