2. ***Disorders of glucose tolerance*** (mild hyperglycemia, gestational diabetes) will be identified through routine glycemic screening as part of usual obstetric care between 24-28 weeks' gestation. Standard care dictates that venous blood is sampled for glucose 1 hour after a 50-gram oral glucose load. If the glucose result is ≥ 130 mg/dL, the participant will be referred for a 100-gram fasting 3-hour OGTT. Normal 3-hour OGTT glucose results include: <95 mg/dL at baseline, <180 mg/dL at 1 hour, <155 mg/dL at 2 hours, and <140 mg/dL at 3 hours.⁷⁷ In this study, we will define glucose intolerance in 2 ways: 1) 1-hour OGTT values ≥ 130 mg/dL (mild hyperglycemia), and 2) two or more abnormal values from the 3-hour OGTT (gestational diabetes). Glucose values ≥ 130 mg/dL are associated with adverse pregnancy outcomes and have been used by us and others to define milder states of glucose intolerance.⁷⁸⁻⁸⁰ We have used this pragmatic approach to collect high-quality OGTT data in prior studies with almost no (<5%) missing values.⁸¹
3. ***Infant birth weight*** will be abstracted from delivery records. Macrosomia will be defined as infant birth weight ≥ 4000 grams. We will calculate sex-specific birth weight for gestational age percentile based on US national data.⁸³ To evaluate intervention safety, we will examine the proportion of small-for-gestational age (SGA) infants by group (e.g., those with birth weights <10th percentile for gestational age).
4. ***Sociodemographics and medical history.*** Participants will self-report age, adverse childhood experiences, food security, race/ethnicity, parity, income and employment, education level,

health status, tobacco use, household size, and marital status. We will abstract medical history from obstetric records, including comorbidities and prenatal/delivery complications.

5. **RE-AIM outcomes.** We will use the RE-AIM framework to evaluate dissemination potential.⁸⁴

Reach will be evaluated in several ways. First, we will work with our WIC colleagues to identify the total number of eligible participants enrolled at WIC during the period of recruitment. Next, we will evaluate the proportion of the eligible WIC population who: 1) are reached by our study activities; 2) are interested in participation; 3) enroll; and 4) are excluded from participation. Lastly, we will assess the representativeness of our sample by comparing the sample's demographic features to that of the target population.

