1. **Primary aim.** We will use Fisher's exact test (for raw intervention effects) as well as multivariable logistic regression (for adjusted intervention effects), testing the effect of treatment group on the odds of excessive gestational weight gain while simultaneously adjusting for covariates discovered to be unbalanced between the trial arms at baseline. We will consider interaction effects of treatment by relevant baseline predictors when needed, (e.g., age, parity, BMI, and gestational age at enrollment), to evaluate the assumption of equal intervention effects between the 2 arms with respect to these covariates. Data will be analyzed using an intention-to-treat (ITT) approach where subjects are analyzed according to their treatment assignment at randomization, regardless of level of engagement. Since an ITT analysis is planned, 2 methods are proposed for accounting for missing data. First, multiple imputation methods will be used to estimate weight at 36-38 weeks' gestation based on intermediate outcomes, mediating variables, and data collected on subjects with complete follow-up.^{87,88} A second approach will utilize model-based analyses with direct maximum likelihood methods.⁸⁹

Additionally, to take advantage of the longitudinal nature of this study, we will treat weight as a continuous measure, employing an advanced mixed-effects modeling approach to estimate individual and mean weight trajectories over time by treatment group. We will supplement weights collected by research staff with available electronic health record prenatal weight data abstracted from WIC and/or participants' obstetric records; we and others have found that the absolute agreement between research and prenatal clinic measured weights is extremely high, providing strong support for exchangeability.^{90,91} Benefits of this modeling approach include: 1) ability to accommodate all available measured prenatal weight data; 2) allowance for varying and/or unequally-spaced intervals between measurements; and 3) high variability in the number of longitudinal assessments expected across subjects. Longitudinal trajectories could be modeled using splines or kernel density.⁹² They will allow for an unbiased estimation of the overall intervention effect on gestational weight gain to better understand non-linear, dynamic changes in weight over time.

2. **Additional aims.** We will use parallel strategies to those described above for secondary and patient-centered outcomes.

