4. **Power and sample size.** Sample size estimates were determined to ensure power for detecting differences in trial arms on the primary study outcome, the proportion of women with excessive gestational weight gain. We used results from

our own preliminary studies along with published data from earlier trials in obese pregnant women to approximate our ability to detect differences in weight gain between trial arms. In our pilot study, Healthy Babies, 37% of intervention participants gained in excess of IOM guidelines compared to 66% of usual care.¹⁹ We recognize, however, that our pilot study's sample size was small, and thus, ***we have made a more conservative assumption for the power analysis in this proposal*** – 15% difference between healthy lifestyle intervention and usual WIC care arms (e.g., prevalence of 40% in the intervention arm vs. 55% in usual care) – based on data that includes a range of between-group differences, from 12% to 30%.^{15,49} Sample sizes of 186 per arm will provide power of at least 0.8 with a 2-sided alpha of 0.05. If the difference is 20% (e.g., 40% vs. 60%), the power will be at least 0.96. Conservatively assuming we will lose 15% for miscarriage or loss to follow-up, the required sample size is 219 subjects per arm or 438 total.

10) Withdrawal of Subjects

Participation in this study is completely voluntary. Participants may refuse to participate or stop participation in this study at any time and it will not affect their present or future care at WIC or Temple University.

11) Privacy & Confidentiality

Information about study subjects will be kept confidential and managed according to the requirements of the Health Insurance Portability and Accountability Act of 1996 (HIPAA). Those regulations require a signed subject authorization informing the subject of the following:

- What protected health information (PHI) will be collected from subjects in this study
- Who will have access to that information and why
- Who will use or disclose that information
- The rights of a research subject to revoke their authorization for use of their PHI.

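### Does the primary analysis need a stated rule for women whose pregnancy ends in loss?

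*Combined protocol and SAP*

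**What the plan says.** Four places in the combined protocol and SAP bear on the point.

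- **Section 9(d)(i), Primary outcome.** Excess gain is a weekly rate above the IOM target "over the study period (from enrollment to end of pregnancy"). Gain is the 36-38 week weight minus the baseline weight. One substitute is given: "In the rare case that a mother delivers her infant before 36-38 weeks" of gestation, the last prenatal weight is taken from the obstetric chart.
- **Section 9(d)(iii)1, Primary aim.** Women are analysed as randomised, by Fisher's exact test and adjusted logistic regression. For missing endpoints, "multiple imputation methods will be used to estimate weight at 36-38 weeks", with direct maximum likelihood as a second approach. Neither method distinguishes reasons for missingness.
- **Section 9(d)(iii)4, Power and sample size.** This is the only place that mentions miscarriage: "Conservatively assuming we will lose 15% for miscarriage or loss to follow-up", 186 evaluable women per arm become 219 randomised.
- **Section 9(d)(iii)2, Additional aims.** "We will use parallel strategies to those described above for secondary and patient-centered outcomes".

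Entry is allowed up to 16 weeks (section 8(d)(i)), so losses after randomisation can occur. Section 10 on withdrawal does not mention them.

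**The concern.** A woman who miscarries has an undefined 36-38 week weight, not merely an unobserved one. Read literally, intention-to-treat plus imputation without exceptions would give her one. The outcome definition offers another route, because it runs to the end of pregnancy: she could be classified on her weekly rate up to the loss. The sample-size section suggests a third, that she drops out of the denominator. The chart-weight rule for early delivery does not naturally reach a miscarriage, and no gestational age marks the boundary.

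If the choice were made after losses by arm were known, the analyst would in effect choose the denominator of the primary result. The general wording for secondary outcomes might seem to extend the difficulty to birth weight. That would include the plan's named safety measure, for which "we will examine the proportion of small-for-gestational age (SGA) infants by group".

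**Working it through.** **Inputs.** From section 9(d)(iii)4: 40% against 55%; 186 evaluable and 219 randomised per arm; 15% attrition; two-sided alpha 0.05; and a cited "range of between-group differences, from 12% to 30" per cent. From section 9(d)(iii)1: Fisher's exact test. The pregnancy-loss rate is not in the documents. It is assumed to be 2%, 5% or 10%, so 219 × 0.02, 0.05 and 0.10 give 4, 11 and 22 women per arm.

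**Step 1: the plan's own figures.** The two-proportion formula gives n₀ = [1.960√(2 × 0.475 × 0.525) + 0.842√(0.55 × 0.45 + 0.40 × 0.60)]² / 0.15² = 172.8. With continuity correction, n = (n₀/4)[1 + √(1 + 4/(0.15 n₀))]² = 185.9, so 186. Then 186/0.85 = 218.8, so 219. Both figures reproduce, and exact Fisher power at 186 per arm is 0.811. The allowance is 219 − 186 = 33 women per arm for miscarriage and loss to follow-up together.

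**Step 2: planned effect, equal losses.** 0.40 × 186 ≈ 74 and 0.55 × 186 ≈ 102. With L losses per arm and x events among 186, the rules are:

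- exclude: x/186
- impute at the arm's own rate: (x + L·x/186)/(186 + L), events rounded
- all not excessive: x/(186 + L)
- all excessive: (x + L)/(186 + L)

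| Rule | Intervention vs control | Difference (points) | p |
|---|---|---|---|
| Exclude | 74/186 vs 102/186 | 15.1 | 0.0050 |
| Impute, L = 4 | 76/190 vs 104/190 | 14.7 | 0.0055 |
| Impute, L = 11 | 78/197 vs 108/197 | 15.2 | 0.0034 |
| Impute, L = 22 | 83/208 vs 114/208 | 14.9 | 0.0032 |
| All not excessive, L = 22 | 74/208 vs 102/208 | 13.5 | 0.0073 |
| All excessive, L = 22 | 96/208 vs 124/208 | 13.5 | 0.0079 |

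With unequal losses of 8 and 14, all counted as not excessive, 74/194 vs 102/200 gives 12.9 points, p = 0.011. Nothing changes at the planned effect.

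**Step 3: the low end of the cited effects.** Take 80/186 vs 102/186, that is 22/186 = 11.8 points. With equal losses of 4, 11 or 22, every rule gives p between 0.0185 and 0.0386. With unequal losses:

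| Losses (intervention, control) | Rule | Counts | Difference (points) | p |
|---|---|---|---|---|
| any | Exclude | 80/186 vs 102/186 | 11.8 | 0.0293 |
| 8, 14 | Impute | 83/194 vs 110/200 | 12.2 | 0.0159 |
| 8, 14 | All not excessive | 80/194 vs 102/200 | 9.8 | 0.0554 |
| 14, 8 | Impute | 86/200 vs 106/194 | 11.6 | 0.0265 |
| 14, 8 | All excessive | 94/200 vs 110/194 | 9.7 | 0.0562 |

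The two p-values above 0.05 come from all-or-none rules that appear nowhere in the plan. Classifying women on their rate up to the loss would have to come almost to one of those extremes to match them:

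- 8 and 14 losses, with 1 of 8 and 2 of 14 excessive: 81/194 vs 104/200, p = 0.044.
- 14 and 8 losses, with 12 of 14 and 7 of 8 excessive: 92/200 vs 109/194, p = 0.045.

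**Step 4: how likely the imbalance is.** Each all-or-none rule is hurt in one direction only. With 14 and 8 losses, counting all as not excessive gives 80/200 vs 102/194, 12.6 points, p = 0.015, which is stronger than excluding. The relevant probability is therefore one-sided. For two independent Binomial(219, loss rate) counts, the probability of a gap of 6 or more in a given direction is 0.030 at 2% loss, 0.113 at 5% and 0.190 at 10%.

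**Step 5: birth weight and SGA.** Section 9(d)(iii)1 names the variable to be imputed, the late-pregnancy maternal weight. Section 9(d)(ii)3 takes birth weight from delivery records and counts SGA among infants. A pregnancy without an infant is outside that wording, so the general sentence on parallel strategies does not call for an invented birth weight.

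**The case for a change.** The best case for acting is that exclusion, however natural, departs from the stated intention-to-treat principle. It conditions on an event after randomisation, and such a departure is best fixed before losses by arm are visible. The remedy would be a few sentences, with no new data and no change to the target of 438. There is also some cost in power under composite rules. Suppose all 15% attrition were pregnancy loss, equal in both arms, with everyone else observed. Counting losses as not excessive would then leave a difference of 0.85 × 15 = 12.75 points and power of 0.78; counting them as excessive would give 0.77.

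What stands is the omission: no section says what happens to these women, and stating a rule would do no harm. The claim of consequence does not stand. The power figures belong to composite rules that the plan does not adopt, at a loss rate that leaves no room for ordinary dropout. Nor is there one right rule to insert. Exclusion, a composite, and classification at the time of loss are all defensible, and experienced statisticians differ on them.

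**Conclusion.** This is missing detail that a competent analyst fills sensibly, not an error. The one mention of miscarriage treats these women as lost, which points to leaving them out. Following the imputation text literally leads to the same conclusion in every case computed: 14.7 to 15.2 points against 15.1 at the planned effect, and p = 0.016 or 0.0265 against 0.029 in the unequal-loss cases near 12 points. Losing significance needs three things together: an effect at the bottom of the cited range, an imbalance of about six women in the unfavourable direction, and an all-or-none or nearly all-or-none rule that the plan does not propose. The safety measure is not exposed.

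The result rests on assumed loss rates of 2% to 10%, and on 186 women per arm with observed outcomes. Imputed women are taken to follow their own arm's rate, although real imputation would also use each woman's earlier weights. The Fisher tests use fixed counts without imputation variance, so the p-values for imputation are illustrative and somewhat optimistic.
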